3.4. Multiplicity Issues, Subgroup Analysis, Interim Analysis, Blinding and Randomisation

All analyses will be presented according to the following subgroups and overall:

- Ig-naïve patients
- Relapsing Ig-pretreated patients

However, statistical tests will be performed only for the overall population (not by subgroup).

No interim analyses will be performed and no p-value will be calculated for each subgroup separately. Therefore, no adjustment for multiplicity will be needed.

Secondary and exploratory analyses are purely descriptive even if p-values will be presented, therefore no multiplicity issues are present. No p-value will be provided by subgroup.

Summary of TEAEs will also be presented by relevant subgroups (e.g., by age group [<65 years and ≥ 65 years], sex, race [white, non-white and unknown], and BMI [<30 kg/m² and ≥ 30 kg/m²]).

Likewise, blinding and randomisation is not applicable in this single-arm, open-label trial.

3.5. Definition of the Protocol Deviations and Population

3.5.1. Populations

The definition of analysis sets is as follows:

- Total Treated Set (TTS): all patients who received at least one administration of the study drug.
- Full Analysis Set (FAS): all TTS patients having an available assessment of the primary efficacy criterion.
- Per Protocol Set (PPS): all FAS patients without any major deviations from protocol (see Section [3.5.2](#)).

If a patient is treated with a non-allowed treatment during the study period, then all efficacy variables measured after the intake of these non-allowed treatments will be censored for the efficacy analyses.

The TTS will be used for the analysis of safety data.

The FAS will be used for the primary analysis of efficacy data and the PPS to test its robustness.

3.5.2. Protocol deviations

The protocol deviations and corresponding categories are defined in the protocol deviation plan as well as their consequence for the inclusion in the different analysis sets. The following protocol deviations categories will be studied:

- Deviations regarding inclusion criteria
- Deviations regarding exclusion criteria
- Deviations regarding the study drug
- Deviations regarding safety assessments
- Deviations regarding assessment of laboratory parameters (including biomarkers)
- Deviations regarding visit windows
- Deviations regarding informed consent
- Deviations regarding forbidden treatments during the study
- Deviations regarding overdose/misuse of study drug
- Other protocol deviations
- Deviations regarding the primary efficacy endpoint
- Deviations regarding other efficacy endpoints
- Deviations regarding exploratory endpoints

- Deviations regarding the ancillary study

All the protocol deviations which occurred during the study will be examined during the final data review meeting. All adjudicated protocol deviations will be presented in data listings.

4. STATISTICAL ANALYSIS

4.1. Disposition of Patients

In order to describe population, descriptive statistics (number, or number and percentages) as well as a listing will be provided for the following patients:

- Patients screened (patients who signed informed consent)
- Patients enrolled
- Patients with a screening failure
- Patients who were re-screened
- Patients who received study treatment (TTS)
 - Patients participating in the ancillary study
 - Patients who completed the study
 - Patients withdrawn early from the study and reasons for study discontinuation [Adverse event (AE), Protocol deviation, Withdrawal of consent, Lost to follow-up, Insufficient response to IMP, Other]
 - Patients withdrawn early due to insufficient response of IMP with reason for insufficient response (INCAT, MRC sum score, R-ODS, Grip strength, CGI-Patient, CGI-Investigator, Clinical examination, Premature termination of IMP) and follow-up treatment (IVIg, Corticosteroids, Immunomodulatory or immunosuppressive agent or Other)
- Patients included in the FAS
- Patients included in the PPS

Percentages for patients enrolled, failed screening or re-screened will be calculated using the number of unique patients screened as the denominator. For the TTS, percentages will be calculated using the number of patients enrolled as the denominator, any other populations will use number of patients within the TTS as the denominator. For screen failure patients, a listing will be produced with the reason for screening failure and the specifications provided by the investigator. For patients who discontinued the study, a listing will be produced with the reasons of study discontinuation and the specifications provided by the investigator. Listings will also be produced for study entry, end of study (EOS) and patient study visits.

4.2. Protocol Deviations

The absolute number of deviations as well as the number and percentage of patients with at least one protocol deviations will be tabulated by deviation category and Minor/Major. Deviation details will be provided in a listing.

4.3. Demographic and Baseline Characteristics

Unless otherwise specified, the baseline value is defined as the last available value before the first IMP course.

The following characteristics will be summarized in patients of the TTS. If the FAS significantly differs (at least 10%) from the TTS, the characteristics will also be summarized in the FAS.

- Demographic characteristics:
 - Age at screening (years)
 - Age in class: [<65 years and ≥ 65 years]
 - Gender
 - Race
- Clinical examination:
 - Weight (kg)
 - Height (cm)
 - Body mass index (BMI) [kg/m^2] ([section 5.7.1](#))
 - BMI in class: [$<30 \text{ kg}/\text{m}^2$ and $\geq 30 \text{ kg}/\text{m}^2$]
- History of CIDP disease:
 - Time since the date of first symptoms (years) ([section 5.7.1](#))
 - Time since the date of diagnosis (years) ([section 5.7.1](#))
 - Time between first symptoms and diagnosis (years) ([section 5.7.1](#))
 - Diagnostic categories of CIDP
 - * Clinical criteria of CIDP (typical / atypical)
 - * Electrophysiological criteria of definite CIDP
 - * Supportive criteria of CIDP
 - Current INCAT disability score (arms, legs and global non-adjusted INCAT scores and global adjusted INCAT score)
- Prior medications
 - Prior medications will be presented by therapeutic subgroup (level 2) and chemical subgroup (level 4) according to version WHO_DDE_B2_DECEMBER_1_2014 of the World Health Organization's (WHO) Anatomical Therapeutic Chemical (ATC) classification system. The term 'prior medication' refers to any medication given up to 2 months before screening or judged relevant by the Investigator.
- Medical and surgical history
 - Medical and surgical history will be classified by preferred term (PT) and system organ class (SOC) using the version 17.1 of the Medical Dictionary for Regulatory Activities (MedDRA).

4.4. Prior and Concomitant Treatment

Prior medications are any medications the patient received up to 2 months before screening or judged relevant by the Investigator. Thus, a prior medication is defined as a medication with a date of screening \leq start date + 2 months. If a medication has a partial start date, the earliest possible date within the partial date is used.

Concomitant medications are any medications the patient received at any time during the study, i.e. from screening to EOS visit. Thus a concomitant medication is defined as a medication with a treatment period which has at least one day in common with the period of screening to EOS visit, i.e.

- Date of screening \leq Start date of medication \leq Date of EOS visit or
- Date of screening \leq End date of medication \leq Date of EOS visit or
- Start date of medication \leq Date of screening and Date of EOS visit \leq End date of medication

If a medication has a partial start date or end date, the earliest possible date within the partial start date is used and the last possible date within the partial end date.

Prior and concomitant medications will be summarized using TTS and will be classified according to version WHO_DDE_B2_DECEMBER_1_2014 of the WHO ATC classification system. Separate tables and listings will be produced for prior and concomitant medications presenting the number and percentage of patients with at least one medication by therapeutic subgroup (level 2) and chemical subgroup (level 4). The tables will be sorted by decreasing incidence of therapeutic subgroup and by decreasing incidence of chemical subgroup within therapeutic subgroup.

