7. PRIOR AND CONCOMITANT MEDICATION

7.1. Prior Medication

The term ‘prior medication’ refers to any medication given up to 2 months before screening.

All relevant prior medications taken within two months prior to screening must be recorded in the patient’s medical file and documented on the appropriate pages of the eCRF. Moreover, any prior medication taken more than two months prior to screening which is, in the opinion of the investigator, clinically relevant to the patient's condition will also be recorded.

The following medications are not allowed before screening because they could interfere with the assessment of study drug efficacy:

- Any other investigational product administered within the last month prior to screening.
- Plasma exchange, blood products or derivatives administered within the last 3 months prior to screening.
- Immunomodulatory or immunosuppressant agents (including but not limiting to cyclophosphamide, cyclosporine, interferon- α , interferon- β 1a, anti-CD20, alemtuzumab, aziathioprine, etanercept, mycophenolate mofetil, methotrexate) or haemopoetic stem cell transplantation administered during the last 12 months prior to screening.
- Systemic corticosteroids therapy if administered with an increasing dosage or introduced, or administered at a dose higher than 10 mg prednisolone per day, or equivalent. Topical corticosteroids are permitted.
- Loop diuretics administered during the last 24 hours before IVIg infusion planned date. In this case, the study drug infusion date will have to be postponed.

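### The SAP's date rule for prior medication does not match its own definition: it counts drugs started on study and leaves out drugs started more than 2 months before screening but taken within the window

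*SAP*

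**What the plan says.** SAP section 4.4 opens with a definition in words: "Prior medications are any medications the patient received up to 2 months before screening or judged relevant by the Investigator". SAP section 4.3, which lists prior medications among the baseline characteristics, uses the same words: the term "refers to any medication given up to 2 months before screening or judged relevant by the Investigator". Protocol section 7.1 agrees on the window. There the term "refers to any medication given up to 2 months before screening", and the recording instruction makes clear that use is what counts: "All relevant prior medications taken within two months prior to screening must be recorded". Earlier drugs are also to be recorded if they matter clinically: "any prior medication taken more than two months prior to screening which is, in the opinion of the investigator, clinically relevant".

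SAP section 4.4 then turns the words into a date rule, presented as their consequence: "a prior medication is defined as a medication with a date of screening" less than or equal to start date plus 2 months. The next sentence deals with incomplete dates, but only at the start: "If a medication has a partial start date, the earliest possible date within the partial date is used".

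The concomitant rule in the same section works differently. It uses both start and stop dates and asks whether the treatment period overlaps the span from screening to the EOS visit by at least a day. Partial starts take the earliest possible date and partial stops the latest. Separate tables and listings are planned for the two classes, on the TTS.

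**The concern.** The words depend on when a drug was taken; the date rule depends only on when it was started. A rule built on the start date alone cannot tell whether a drug was in use during a window. Because this one has no limit at screening, it also lets in treatment that began later.

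What is at stake is the accuracy of the prior-medication table and listing. A reader would expect them to show what patients were taking on entry. Produced from the rule as written, they would mix on-study treatment with baseline therapy and leave out established therapy.

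**Working it through.** No figure in the plan needs reproducing; the check is one of date logic. Let S be the screening date, A the start date and B the stop date of a drug.

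- **Words (SAP 4.3 and 4.4, Protocol 7.1):** A < S and B ≥ S − 2 months, or flagged relevant.
- **Date rule (SAP 4.4):** S ≤ A + 2 months, which is A ≥ S − 2 months. B does not appear, there is no condition A < S, and there is no relevance term.
- **Concomitant rule (SAP 4.4):** A lies between S and EOS; or B lies between S and EOS; or A ≤ S and B ≥ EOS.

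Setting relevance aside, the words and the date rule disagree in two regions.

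1. A ≥ S (started on study). The date rule says prior; the words say not.
2. A < S − 2 months and B ≥ S − 2 months (started earlier, taken into the window). The words say prior; the date rule says not. This region splits:
   - B ≥ S: still taken at screening, so the concomitant rule catches the drug.
   - S − 2 months ≤ B < S: stopped inside the window. All three concomitant conditions fail, so the drug meets neither rule.

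They agree when S − 2 months ≤ A < S (both prior) and when B < S − 2 months (both not prior).

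Eight examples, with an assumed 28 weeks from screening to EOS and ongoing drugs given a stop date after EOS:

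| Drug | Date rule: prior? | Words: prior? | Concomitant? |
|---|---|---|---|
| Started 5 years before screening, ongoing | No | Yes | Yes |
| Started 3 months before, stopped week 4 | No | Yes | Yes |
| Started 3 months before, stopped 1 month before | No | Yes | No |
| Started 1 month before, stopped 1 week before | Yes | Yes | No |
| Started 1 month before, ongoing | Yes | Yes | Yes |
| Started week 12 | Yes | No | Yes |
| Started on the EOS day | Yes | No | Yes |
| Started 5 months before, stopped 4 months before | No | No | No |

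A grid of start and stop dates in 3-day steps gave the same result. The date rule classed as prior all 3510 of 3510 combinations starting between screening and EOS. It classed as prior 0 of 9804 combinations that started more than 2 months before screening and were still running at screening; all 9804 met the concomitant rule. These are counts of date combinations, not forecasts of patients.

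Two further points follow from the text. Taking the earliest possible date for a partial start can only move drugs out of the prior class under this rule. And previous Ig in the relapsing pretreated group, which inclusion criterion 4b requires to have ended at least 3 months before screening, can count as prior only through the relevance clause that the date rule drops.

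**The case against.** The best defence is that the inequality should be read with the sentence it implements. A drug first given at week 10 was plainly not received before screening, and a programmer might follow the words. Protocol section 8.2.1 also lists prior medications at the screening visit separately from ongoing concomitant treatments, so the formula might never be run on on-study records. The documents do not show the eCRF or dataset structure, so this cannot be excluded. The counts above therefore describe the rule as written, not a demonstrated output. But the SAP presents the inequality as its definition, and a definition with two readings needs correcting. The screening-visit argument also does nothing for drugs that started earlier and were taken into the window.

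A reader might infer three stronger things, none of which the documents support.

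- *Long-standing background therapy is lost from the report.* Drugs still taken at screening, such as a permitted ongoing corticosteroid, appear in the concomitant table, on the same set and at the same ATC levels. Only drugs started more than 2 months before screening and stopped within those 2 months miss both tables. SAP section 5.1 also promises that all data will be listed, although separate prior and concomitant listings built on these rules would have no place for such a record.
- *The table supports comparability with the historical control.* No section gives it that use. The control enters the analysis only as a fixed rate of 33.3%.
- *The efficacy result is affected.* The primary test, the sample size and the censoring after non-allowed treatment (SAP sections 3.5.1, 4.6 and 4.6.1) do not refer to prior status. The treatment-change endpoint relies on a study physician's review of corticosteroids and immunosuppressive drugs (SAP 4.6.2).

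**Conclusion.** The point holds as a mismatch between a definition and its formula. Applied literally, the rule puts every on-study start into the prior-medication table and listing. It excludes every drug started more than 2 months before screening, including those taken within the window. Of these last, drugs still taken at screening remain visible as concomitant; drugs stopped in the 2 months before screening fall out of both tables.

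This is minor: it affects descriptive prior-medication outputs and no inference. How many patients or records are involved cannot be told from the documents. The conclusion assumes that the inequality is programmed as written on all medication records; it does not depend on the assumed 28-week span.

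**What to change.** Replace the date rule in SAP section 4.4 with: start date before screening, AND stop date on or after screening minus 2 months or ongoing; OR flagged relevant by the Investigator. Use the earliest possible date for partial start dates and the latest possible date for partial stop dates, as the concomitant rule already does. A drug started before screening and continued into the study would then count in both classes, as the two verbal definitions imply.

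Replacing the start date by the stop date in the present inequality would not be enough: with no upper limit at screening, on-study drugs would still count as prior.

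The cost is about one line of SAP text and the matching line of code. The change restores the documents' own definition and alters no efficacy analysis.

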4.5. Compliance

Study treatment compliance will be summarized using the TTS. Treatment compliance will be presented by course, by infusion and by patients as described below. The term Planned refers to the treatment dose and frequency planned at enrollment. The term Prescribed refers to the treatment dose and frequency reported at each IMP course and infusion.

4.5.1. Course/infusion level

Compliance will be described on the course level using the following criteria:

- Prescribed course dose (g/kg) = Theoretical course dose (g/kg) \pm 20%
Theoretical course dose is defined according to the protocol as
 - a. 2 g/kg at the first course and 1 g/kg at subsequent courses for patients with a BMI <30 kg/m²
 - b. 1.6 g/kg at the first course and 0.8 g/kg at subsequent courses for patients with a BMI ≥ 30 kg/m²
- Time since previous course = 3 weeks \pm 7 days
- Courses administered within
 - a. 2 to 5 days (first course)
 - b. 1 to 3 days (subsequent courses)
- Duration of the flow rate of the first course infusion remains unchanged for at least 25 minutes
- Flow rate of the first infusion of a course ≤ 0.5 mL/kg/h
- Overall course compliance: A course is compliant if all above course compliance criteria are fulfilled and all infusions of the course are compliant

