3.1.4. Treatment

Patients who meet all the eligibility criteria will receive one dose of study drug at 2 g/kg over 2 to 5 days. Three (3) weeks later, they will start to receive 7 doses of study drug at 1 g/kg over 1 to 2 day(s) each, every 3 weeks (+/- 7 days).

Investigators or Study Nurses will call patients 4 days (+/-1 day) after the end of each study treatment course to document potential AEs and TAAEs (see Section [8.2.4](#)).

Duration of the treatment period will be approximately 21 weeks.

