6.1.3. Administration of study drug to patients

6.1.3. 1. Study drug dosage and treatment schedule

The study drug dosage should be at 2 g/kg for the first administration, then at 1g/kg for the rest of the study.

For patients with BMI ≥ 30 kg/m², the dose must be reduced by 20% i.e 1.6 g/kg for the first administration and 0.8 g/kg for the rest of study.

It is not recommended to change the study drug dose or frequency of administration during the study.

Under no circumstances will the Investigator/Hospital Pharmacist allow the study drug to be used other than as directed by the protocol.

Before any infusion, the Investigator will rule out any study drug over or under dosage in regards to patient's body weight and protocol requirements.

6.1.3. 2. Method of administration

Before administration to a patient, the Investigator will check that the label corresponds to his/her prescription for the patient (study number, patient number, study drug dose).

Study drug will be administered with an infusion pump.

The infusion flow rate must be compliant with the Investigator's Brochure of I10E.

For the first day of any study drug course, the initial flow rate will not exceed 0.5 mL/kg/h during the first 30 minutes. If well tolerated, the rate of administration may be increased up to 1 mL/kg/h during 30 minutes, then - at the Investigator's discretion - gradually increased up to 2, 4 and 6 mL/kg/h as a maximum flow rate.

In patients older than 65 years, the maximum infusion flow rate should be 2 mL/kg/h.

On the subsequent days of any study drug course, the flow rate is at the Investigator's discretion (up to 6 mL/kg/h; up to 2 mL/kg/h for patients older than 65 years).

6.1.3. 3. Traceability, accountability and documentation

Each study drug course should be documented in the patient's medical file, including doses, time and flow rate changes.

The prescribed dose, the date and time of administration and the exact dose administered will be recorded in the eCRF.

The Sponsor will provide specific forms for study drug accountability, which will be kept up-to-date by the Hospital Pharmacist throughout the study. At the end of the study, it must be possible to reconcile the number of study drugs sent by the drug distributor with the number of study drugs delivered to patients and the number of unused study drugs.

6.1.3. 4. Compliance

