Compliance with treatment is defined as dose(s) administered within 20% of the prescribed dose(s). Both prescribed and administered doses will be recorded in the eCRF.

As the study drug will be administered only under the direct supervision of a physician familiar with the requirements of the study protocol, compliance should not be an issue. Nevertheless, the reason for any non-compliance must be recorded in the eCRF.

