12.8.2. Treatment Compliance

The following compliance criteria will be described:

- Prescribed course dosage included in the ranges allowed by the protocol
- Course frequency included in the ranges allowed by the protocol
- Courses administered at each visit.
- Ratio administered dose / prescribed dose within 20%.

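### SAP 4.5.1 omits the protocol's administered-to-prescribed dose criterion, leaves infusion compliance undefined and uses different infusion limits, so reported compliance will not measure what the protocol defines

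*SAP*

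**What the plan says.** Protocol 6.1.3.4 gives the definition: "Compliance with treatment is defined as dose(s) administered within 20% of the prescribed dose(s"). It adds that both doses are recorded in the eCRF. Protocol 12.8.2 lists the same quantity among the compliance criteria to be described: "Ratio administered dose / prescribed dose within 20"%.

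SAP 4.5.1 has one dose criterion, "Prescribed course dose (g/kg) = Theoretical course dose (g/kg"), with a tolerance of 20% either way. The theoretical dose is the protocol regimen, reduced for BMI of 30 kg/m² or more. SAP 4.5 explains its terms thus: "The term Prescribed refers to the treatment dose and frequency reported at each IMP course and infusion".

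The other SAP criteria are the interval between courses, the course length, how long the starting flow rate is held, and a flow-rate limit of 0.5 mL/kg/h for the first infusion of a course. A course is compliant overall if it meets all of these and all its infusions are compliant. A patient is compliant if every course is (SAP 4.5.2).

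On course length, the SAP allows "1 to 3 days (subsequent courses"), where protocol 3.1.4 has "7 doses of study drug at 1 g/kg over 1 to 2 day(s) each". On the starting rate, the SAP asks: "Duration of the flow rate of the first course infusion remains unchanged for at least 25 minutes". Protocol 6.1.3.2 says that "the initial flow rate will not exceed 0.5 mL/kg/h during the first 30 minutes" on the first day of a course, with stepwise increases allowed afterwards.

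**The concern.** Prescribed against theoretical dose tells us whether the order matched the regimen. Administered against prescribed dose tells us whether the patient received what was ordered. The protocol plans to describe both; the SAP's listed criteria contain only the first. If an infusion is cut short, the listed dose criterion need not register it. The SAP 4.5.2 listing shows non-compliant courses and infusions against the same criteria, so it need not register it either.

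The overall rule adds a second problem. It depends on infusion compliance, which has no definition, so whoever programs the table must invent one or ignore the condition. The course-length and flow-rate lines also differ from the protocol, and SAP 4.10, whose purpose is to record changes from the protocol, is silent on all of it. At stake is whether the compliance rate in the study report can be read as the protocol's measure.

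**Working it through.** **The SAP's own figures.** The theoretical doses for BMI of 30 kg/m² or more reproduce: 2 × 0.8 = 1.6 g/kg and 1 × 0.8 = 0.8 g/kg, as in protocol 6.1.3.1. The defect is in which doses are compared, not in these numbers.

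**Side by side.**

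| Item | Protocol | SAP 4.5.1 | In SAP 4.10? |
|---|---|---|---|
| Prescribed dose against regimen | listed (12.8.2) | listed, ±20% | not applicable |
| Administered / prescribed dose within 20% | definition (6.1.3.4), listed (12.8.2) | absent | no |
| Infusion-level compliance | not used | required, undefined | no |
| First course length | 2 to 5 days | 2 to 5 days | not applicable |
| Later course length | 1 to 2 days | 1 to 3 days | no |
| Starting rate held for | 30 min | 25 min | no |
| 0.5 mL/kg/h limit applies to | first 30 min of the first day | first infusion of a course, as worded | no |

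**A partly given course.** Take a course prescribed at 1 g/kg of which 0.5 g/kg is given (theoretical dose 1 g/kg).
- Listed SAP criterion, with prescribed meaning ordered: 1 / 1 = 1.00, within 0.80 to 1.20, passes.
- Protocol criterion: 0.5 / 1 = 0.50, outside 0.80 to 1.20, fails.
- Listed SAP criterion, if prescribed means the dose reported as given: 0.5 / 1 = 0.50, fails.

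The SAP does not settle which reading applies. SAP 4.5 ties the term to what is reported at each course and infusion, and SAP 4.7.1.3 describes one volume as both prescribed and administered. The undefined infusion condition could change the outcome again.

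**Effect of restoring the ratio.** With both checks, a compliant course has an administered dose between 0.8 × 0.8 = 0.64 and 1.2 × 1.2 = 1.44 times theoretical. That is 0.64 to 1.44 g/kg against 1 g/kg, and 1.28 to 2.88 g/kg against 2 g/kg. With prescribed read as ordered, the listed SAP criteria set no explicit bound on the administered dose. This is arithmetic on the stated tolerances, not a view on acceptable doses.

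**The flow-rate line read literally.** The concentration is 100 mg/mL, so 1 g/kg is 10 mL/kg and 2 g/kg is 20 mL/kg. Assuming one infusion a day and equal daily volumes, an infusion held at 0.5 mL/kg/h would last:
- 1 g/kg in one day: 10 / 0.5 = 20 h.
- 1 g/kg over two days: 5 / 0.5 = 10 h per day.
- 2 g/kg over two days: 10 / 0.5 = 20 h per day.
- 2 g/kg over five days: 4 / 0.5 = 8 h per day.

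The protocol permits increases up to 6 mL/kg/h (2 mL/kg/h in patients older than 65). Any first infusion that uses them fails the literal line.

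**Reach.** 42 patients × 8 courses = 336 courses at most. The documents give no rate of partly given courses. For illustration only, suppose a fraction q of courses, independently, fails nothing but the ratio check. The share of 8-course patients passing that item is (1 − q)^8: 92.3% at q = 1%, 85.1% at 2%, 66.3% at 5% and 43.0% at 10%. Without the check it is 100%.

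**The case against.** The best defence is that under-dosing will be visible anyway, and most of this stands. SAP 4.7.1 summarises administered dose by patient, course and infusion. It also lists all infusions of the course for patients with an interrupted, discontinued or slowed infusion. SAP 4.6.2 counts a course as a change in CIDP treatment if its average dose, derived in SAP 5.7.3 from the dose actually given, is not within 5% of theoretical. The half-given course above, at 0.50 of theoretical, falls outside 0.95 to 1.05. Adverse events are tabulated by action taken. Infusions are supervised by a physician, and the protocol expects compliance not to be an issue. None of these outputs, however, reports the rate that protocol 12.8.2 says will be described.

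It is also fair that the SAP has not swapped one definition for another: prescribed dose against protocol range is itself a 12.8.2 criterion. What is missing is the ratio. It may have been meant to sit inside the infusion condition; if so, the SAP must say so.

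A reader might infer that compliance will be overstated. The documents do not support that. The missing ratio, the extra day and the shorter hold time are looser than the protocol. The literal flow-rate line is stricter, and so in form is requiring every criterion on every course, because the protocol's definition concerns dose alone. A reader might also infer that the flow-rate limit itself differs. It does not: 0.5 mL/kg/h is the same in both documents, and what differs is the hold time and the part of the infusion covered. SAP 4.7.1 names an initial flow rate explicitly, so 4.5.1 may have intended that, but its wording does not say so.

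**Conclusion.** The point holds as an undeclared mismatch between SAP and protocol. SAP 4.5.1 leaves out the protocol's compliance criterion, rests overall course compliance on an undefined infusion condition, and differs on later-course length (3 against 2 days at the upper end), starting-rate duration (25 against 30 minutes) and the span of the 0.5 mL/kg/h limit. The reported rate would therefore not be the one the protocol defines, and the direction of the difference cannot be told.

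The half-dose example shows that a partly given course could pass the listed dose criterion, not that it must, since that depends on what prescribed means and on the missing infusion rule. The patient-level percentages rest on assumed failure rates and independence, and are not estimates for this trial.

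The reach is limited. Compliance is a descriptive summary on the Total Treated Set and enters no hypothesis test, so the primary analysis and sample size are unaffected. One might suppose that it decides membership of the Per Protocol Set, but SAP 3.5.2 assigns that to a separate deviation plan. The correction is still worth making, because it concerns a planned result and uses data already collected.

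**What to change.** - Add administered / prescribed dose within 20%, per course, to SAP 4.5.1 and to the rule for overall course compliance.
- State the infusion-level criterion on which that rule depends.
- Use prescribed and administered consistently in SAP 4.5 and 4.7.1, so that each refers to one recorded quantity.
- Reconcile the course-length and starting-rate passages of SAP 4.5.1 with protocol 3.1.4 and 6.1.3.2, including whether the 0.5 mL/kg/h line covers the initial rate or the whole first infusion. No view is taken here on which limit is right.
- Record in SAP 4.10 any difference from the protocol that is kept, including an intended tolerance.

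The cost is SAP wording and minor programming. Both doses are already in the eCRF, so no new data are needed. The reported compliance figure may change, in either direction.
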